10.3.4 Safety Analyses

Descriptive statistics will be used to summarize side effects of the intervention at POD 0, POD 1, and POD 27 as well as adverse events as reported by participant or observed by the investigator at POD 1, POD 27, POD 55, and POD 83.

10.3.5 Adherence and Retention Analyses

Adherence will be tracked and reviewed using REDCap as well as Epic for ketamine administration. Participant retention and any reasons for discontinuation will be carefully recorded and summarized.

10.3.6 Baseline Descriptive Statistics

Descriptive statistics will be used to summarize the demographic and baseline characteristics, with mean and standard deviation for continuous variable, or frequency and percentage for categorical variables. If continuous variables are skewed, the median and inter-quartile range will be used as well. To test differences in the demographic and baseline characteristics between the two arms, clinical variables that are continuous will be compared using either two sample t-test if normally distributed or Wilcoxon's ranksum test otherwise and categorical variables will be compared using Chi-squared or Fisher's exact test. Unbalanced baseline variables will be determined by both statistical and clinical significance.

10.3.7 Planned Interim Analysis

Not applicable to our study.

10.3.7.1 Safety Review

As iterated above, this study may be temporarily suspended or prematurely terminated if there is sufficient reasonable cause. Proposed reasons for stopping study enrollment or the study intervention include determination of unexpected and significant risk to participants, demonstration of efficacy or futility that warrants stopping, and insufficient compliance to protocol. Adverse effects will be monitored carefully in the PACU, and then again on POD 1, POD 27, POD 55, and POD 83.

10.3.8 Additional Sub-Group Analyses

All analyses are provided above; there will not be additional sub-group analyses.

10.3.9 Multiple Comparison/Multiplicity

Not applicable to our study.

10.3.10 **Exploratory Analyses**

All analyses are specified as above; there are not planned exploratory analyses.

May 2, 2022 Version: 1.23

Page 25

10.4 Sample Size

This is a pilot study with limited resources so that it is not powered to detect a hypothesized effect size for VAS. We expect to randomize 15 participants to each arm. With 15 subjects per arm, we have 80% power to test an effect size of 1.1 with a significance level (alpha) of 0.05 using a two-sided Wilcoxon's rank-sum test assuming data are generated from normal distributions.

10.4.1 Enrollment/Randomization/Masking Procedures

The subjects will be randomized in a 1:1 ratio. The treatment subjects will receive 0.6 mg/kg of the study drug, and the control subjects will receive an equal volume of saline. Participants will be randomized with random size permuted blocks, blinded with respect to treatment assignments. [name] (the PI) will generate the randomization list.

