Objectives	To explore the effect of a sub anesthetic dose of ketamine (0.6 mg/kg) vs. saline control on postoperative pain and recovery in chronic pelvic pain patients who have undergone robotic removal of endometriosis.
Methodology	Randomized, double blinded, placebo-controlled trial
Endpoint(s)	Visual Analogue Score (VAS) Endometriosis Health Profile-30 Opiate use General Anxiety Disorder-7 (GAD-7) Montgomery-Asberg Depression Rating Scale (MADRS) Douleur Neuropathique 4 Questions (DN-4) Side Effects Adverse Events
Study Duration	Approximately 10 months
Participant Duration	Approximately 4 months
Duration of IP administration	At least 30 minutes at one time point
Population	Adult women, aged 18-65, with chronic pelvic pain defined as self-reported moderate to severe pelvic pain for > 6 months and scheduled for robotic removal of endometriosis at NYU Langone Health.
Study Sites	NYU Langone Health – Tisch Hospital
Number of participants	30 total participants expected to enroll (15 in treatment group, 15 in control group)
Description of Study Agent/Procedure	Ketamine[(+/-)-2-(2-chlorophenyl)-2-(methylamino)-cyclohexanone] is a white, crystalline powder or clear liquid. Ketamine at a dose of 0.6 mg/kg will be administered intravenously (IV) while the participant is recovering in the PACU. The study drug will be administered over at least 30 minutes at one time point and will be administered after subject has been deemed to be stable (hemodynamically stable, awake) by the study team on POD 0.
Reference Therapy	Saline. Saline is a prescription medicine used for fluid and electrolyte replenishment for intravenous administration. This is placebo drug in this study.
Key Procedures	IV administration of ketamine or saline Self-reported questionnaires Medical records review (opioid use and dosage assessments)
Statistical Analysis	Descriptive statistics will be used to summarize continuous variables. The normality of the distributions for continuous variables will be tested using Q-Q plots and Shapiro–Wilk tests. Differences between arms will be compared with two-sample t-test if outcome is normally distributed or with Wilcoxon's rank-sum test otherwise.

84, POD 83

Schematic of Study Design

Final Assessments

Refer to Section 20

May 2, 2022 Version: 1.23

1 Key Roles

Principle Investigator:
[name]
Assistant Professor, Department of Obstetrics and Gynecology
NYU Grossman School of Medicine
[name]
[contact]
[contact]

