2.4.2 Protection against Risks

Given that ketamine will be given in the recovery room, all participants will be monitored by the study care team and PACU physicians for any of the effects mentioned above. To minimize the risk of physiological effects and cardiovascular side effects, the single bolus ketamine dose will be given over at least a 30-minute period. For the risks of psychomimetic side effects, such side effects may be treated with reassurance.

The investigators have many layers of protection to minimize the risk of inadvertent release of protected health information. The methods for de-identification of data will mitigate this risk. We will take all necessary precautions to maintain complete confidentiality of data and prevent unauthorized access to the data. Data will only be collected from subjects who consent and whose physicians deem safe to proceed with data collection. Participants will be allowed to exit the study at any time. Participants who withdraw consent will be counseled that their withdrawal only affects uses and sharing of information after their written request to withdraw authorization has been received, and that their authorization may not be withdrawn for uses or disclosures that have previously been made or need to be made to complete analyses or report data from the research. For the confidentiality of randomization, only the physician administering the study drug will know which group the subject(s) is/are in for both the experimental and control group.

May 2, 2022 Version: 1.23

May 2, 2022 Page 8

All data and records generated during this study will be kept confidential in accordance with institutional policies and HIPAA on subject privacy. The study investigators will not use such data and records for any purpose other than conducting the study. Privacy protection procedures are in place and good clinical practice guidelines will be followed throughout the study to minimize the risks associated with breach of confidentiality. This risk will be minimized by strict compliance with HIPAA procedures for securing PHI. Information that could be used to identify the subject will only be shared with researchers who have approval of the IRB.

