4.1 Description of Study Design

This is a phase 1 randomized, double-blind, placebo-controlled, two-arm parallel, single-center study.

30 subjects (15 in each arm) will be accrued. Randomization lists will be sent only to the study physician administering study drug. Participant and assessor of outcome measures will be blinded. The surgeon, anesthesiologist, and the research team members conducting the follow up visits will not know which group the subjects are assigned to. Only the physician administrating the study will be aware of whether ketamine or placebo is administered, and this provider will not be a part of any outcome measure data collection. The investigators conducting and reviewing the outcome measures will be blinded.

Adult women, aged 18-65, with chronic pelvic pain (defined as moderate to severe self-report > 6 months) will be screened for eligibility to participate in this study. Prospective subjects will be recruited, screened, and consented prior to surgery. On the day of the surgery, Eligible subjects will be randomized to one of the two groups in a 1:1 ratio to receive either intravenously (IV) ketamine (0.6 mg/kg) or matching equal dose of placebo. Subjects will receive either the study drug or placebo while recovering in the post anesthesia care unit (PACU) on the day of the surgery after subject has been deemed to be stable

May 2, 2022 Version: 1.23

2, 2022 Page 9

(hemodynamically stable, awake). The study drug or placebo will be administered by study physicians who are anesthesiologists. The study physician will administer the study intervention via an intravenous pump to deliver 0.6 mg/kg ketamine or equal volume saline over at least 30 minutes.

Participation in the study will not alter the subject's surgical or anesthetic care, post-anesthetic care, or standard of care on the floor. All subjects will also receive standard post-anesthetic monitoring and care, as well as routine care after transferring out of the PACU. There is no restriction on the use of other analgesics throughout this study. Subjects are followed, and endpoints (see below) are collected from subject reports as well as from medical charts (opioid use).

Patient demographics recorded include age, date of birth, race, MRN, gender, ethnicity, participant enrollment location, zip code, and disease site.

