5.7 Participant Withdrawal or Termination

5.7.1 Reasons for Withdrawal or Termination

Participants are free to withdraw from participation in the study at any time upon request for any reason, and without repercussion. Participants who withdraw consent will be counseled that their withdrawal only affects uses and sharing of information after their written request to withdraw authorization has been received, and that their authorization may not be withdrawn for uses or disclosures that have previously made or need to be made to complete analyses or report data from the research. For the confidentiality of randomization, only the physician administering the study drug will know which group the subject(s) is/are in for both experimental and control group. All data and records generated during this study will be kept confidential in accordance with institutional policies and HIPAA on subject privacy. The study investigators will not use such data and records for any other purpose other than conducting the study. Privacy protection procedures are in place and good clinical practice guidelines will be followed throughout the study to minimize the risks associated with breach of confidentiality. This risk will be minimized by strict compliance with HIPAA procedures for securing PHI. Information that could be used to identify the subject will only be shared with researchers who have approval of the IRB.

The investigator and sponsor have the right to discontinue a subject from study treatment or withdraw a subject from the study at any time. If a subject is discontinued from the study at the discretion of a PI or other delegated individual, the reason for discontinuation procedures will be noted in the subject's research record.

An investigator may terminate participation in the study if, but are not limited to:

Subject withdrawal of consent at any time

May 2, 2022 Version: 1.23

Page 13

- Disease progression
- Intolerable toxicity
- Any medical condition that the investigator or sponsor determines may jeopardize the subject's safety if the subject continues treatment with the study drug
- The investigator or sponsor determines it is in the best interest of the subject
- Failure of the subject to adhere to protocol procedure requirements
- Study termination by sponsor

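### The PI generates the randomization list and no visible text separates the PI from the sequence, so allocation concealment is unsecured, though not shown to be broken

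*Combined protocol and SAP*

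**What the plan says.** On who makes the list, Section 10.4.1 is explicit: "the PI) will generate the randomization list". The sentence just before it describes the method: "Participants will be randomized with random size permuted blocks, blinded with respect to treatment assignments". It does not say who is blinded or by what means.

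On who knows the arm, three sections agree with one another:
- Section 2.4.2 (Protection against Risks): "only the physician administering the study drug will know which group the subject(s) is/are in for both the experimental and control group".
- Section 5.7.1 repeats this almost word for word.
- Section 4.1 says the same in other terms and adds: "Randomization lists will be sent only to the study physician administering study drug". It also states that the surgeon, the anesthesiologist, the follow-up staff and the investigators who conduct or review outcome measures are blinded.

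On the PI's other duties, Section 16.1 has the PI, with the other investigators, oversee screening, recruitment, visits and procedures. Section 5.4 has the PI, with research staff, answer prospective subjects' questions. Section 5.7.1 allows discontinuation at the discretion of the PI or a delegate. Section 8.2.3 has the PI decide whether an adverse event was expected.

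**The concern.** Whoever generates an unmasked list can know every upcoming assignment. Allocation concealment exists to keep that knowledge away from anyone who can influence which patients enter, stay in or are replaced. Here one person is given the first role by 10.4.1 and shares in the second under 16.1 and 5.7.1.

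The stake is selection before randomization. If a subject can leave between consent and POD 0 while someone with a say in that decision could know the next arm, the groups may differ at baseline in ways that randomization is meant to prevent. An intention-to-treat analysis (10.2) does not repair this, because such subjects were never randomized. A secondary stake is the PI's own blinding in a trial described as double-blind.

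**Working it through.** The plan gives no figure on this point. The power statement in 10.4 (80% with 15 per arm at an effect size of 1.1) does reproduce, at 79.6% by simulation of the exact rank-sum test, but it has no bearing on concealment. The check is therefore a comparison of sections.

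**Step 1. Is the PI a dosing physician?** Section 4.1 says: "The study drug or placebo will be administered by study physicians who are anesthesiologists". Section 1 (Key Roles) places the PI in obstetrics and gynecology. On the visible text these are different people, so the statements that only the dosing physician knows the arm do not cover the PI.

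**Step 2. Does any stated safeguard separate the PI from the sequence?**

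| Safeguard | Where | What it does | Bars the list's author? |
|---|---|---|---|
| Random block sizes | 10.4.1 | Makes guessing harder for others | No |
| List sent to the dosing physician alone | 4.1 | Limits recipients | No |
| Randomization described as blinded | 10.4.1 | States intent; no person or mechanism named | Not as written |
| Surgeon and outcome investigators blinded | 4.1 | States intent; no mechanism | Not as written |
| Randomization on the day of surgery | 4.1, 7.2.3 | Delays assignment | No, if the list already exists |

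No visible text mentions coded arms, sealed envelopes, central allocation or an independent holder of the list.

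**Step 3. Is there a period in which knowledge could affect entry?** Section 5 sets consent between two months and 2 days before surgery. Section 7.2.3 places randomization on POD 0. Within that interval, 5.7.1 lets an investigator end participation because an exclusion criterion is newly found, or on broader grounds: "The investigator or sponsor determines it is in the best interest of the subject". Section 5.7.2 allows replacements.

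**Step 4. Can the effect be sized?**
- The Protocol Summary expects 30 to enroll, and Sections 2.3 and 4.1 have 30 accrued. Surplus over 30: 30 − 30 = 0.
- Section 5.6 enrolls about 50 to maintain 30. Surplus: 50 − 30 = 20, and 20/50 = 40%.

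The two sets of figures conflict. Even the larger one counts losses for any cause at any stage, before or after randomization. Neither measures exits that anyone could steer, and neither measures bias in the VAS.

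**The case against.** **Generating a list is not the same as knowing a subject's group.** Sections 2.4.2 and 5.7.1 concern knowledge of the group, 4.1 concerns receipt of the list, and 10.4.1 concerns its creation. They collide only if the PI reads or keeps the list and can match positions to subjects. This stands: the text leaves an inconsistency unresolved and does not prove a breach.

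**The plan states an intent to blind and records exits.** Section 5.7.1 has the reason noted whenever a subject is discontinued at the PI's discretion, and 10.3.5 has reasons recorded and summarized. Neither is limited to the period after randomization. The pre-surgery exclusion route is also tied to a listed criterion. This stands as a partial safeguard: it makes exits auditable. It does not prevent them, and a recorded reason cannot show whether the next assignment was known.

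**Downstream effects are limited.** The VAS is self-reported, follow-up staff are stated to be blinded, and analysis after randomization is by intention to treat. Adverse events are documented regardless of relationship (8.3), the examining clinician grades causality (8.2.2), the safety analysis is descriptive (10.3.4), and this is a pilot not powered for a hypothesized effect (10.4). All of this stands and keeps the point from being graver. Pilot status does not remove it: the plan still tests efficacy at two-sided p<0.05 (10.3.1), and selection at entry is not cured by sample size.

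**Two stronger readings are tempting.** A reader might infer that the PI is unblinded and concealment has failed. The documents do not say that the PI retains or consults the list, so this is not supported. A reader might also infer from 5.6 that up to 40% of enrolled subjects could be selectively removed. That figure rests on one section, conflicts with the 30 given elsewhere, includes all attrition, and would require no loss after randomization. It is not supported either.

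**Conclusion.** The point holds as an unreconciled rule with a missing safeguard. Followed as written, 10.4.1 puts the sequence in the hands of someone who is not a dosing physician on the visible text and who has a say in entry and discontinuation before POD 0. That does not fit the statements in 2.4.2, 4.1 and 5.7.1. Allocation concealment and the PI's blinding are unsecured; neither is shown to be broken.

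The size of any bias cannot be stated. Confidence is high that the sections are unreconciled; no claim is made that concealment failed in practice.

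The conclusion assumes that the PI is not one of the dosing anesthesiologists and that no barrier is described in text that is not visible, including what follows Key Roles. The matter should be fixed because the repair is specific and cheap.

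**What to change.** Amend 10.4.1 as follows:
- Remove the PI as generator.
- Name an existing person with no role in recruitment, dosing, outcome assessment or adverse-event classification to generate and hold the list, for example an otherwise uninvolved statistician or a data-core member.
- State that the PI has no access to the list wherever it is stored. Section 11 gives the PI access to the study database, so a list kept there would need to be blocked.

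Align 2.4.2, 4.1 and 5.7.1 so that they name the same people as knowing the assignments, including the list-holder.

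If a list already exists, have the unused part regenerated independently and document who has seen it.

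Optional and secondary: release assignments to the dosing physician one at a time, after eligibility is recorded, instead of sending the whole list.

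The cost is a short amendment with IRB approval (13.2) and minor set-up work for the list-holder. Sample size, visits, dosing and analysis do not change.

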10.4.2 Evaluation of Success of Blinding

The subject will be asked if they know what group they were placed in at POD 1. If they are unsure that will be evaluated as successful blinding.

10.4.3 Breaking the Study Blind/Participant Code

In this double-blind study, the blind will not be broken.

11 Source Documents and Access to Source Data/Documents

Source data is all information, original records of clinical findings, observations, or other activities in a clinical trial necessary for the reconstruction and evaluation of the trial. Source data are contained in source documents. Examples of these original documents, and data records include: hospital records, clinical and office charts, laboratory notes, memoranda, subjects' diaries or evaluation checklists, pharmacy dispensing records, recorded data from automated instruments, copies or transcriptions certified after verification as being accurate and complete, microfiches, photographic negatives, microfilm or magnetic media, x-rays, subject files, and records kept at the pharmacy, at the laboratories, and at medico-technical departments involved in the clinical trial. It is acceptable to use CRFs as source documents. If this is the case, it should be stated in this section what data will be collected on CRFs and what data will be collected from other sources.

The study case report form (CRF) is the primary data collection instrument for the study. All data requested on the CRF must be recorded. All missing data must be explained. If a space on the CRF is left blank because the procedure was not done or the question was not asked, write "N/D". If the item is not applicable to the individual case, write "N/A". All entries should be printed legibly in black ink. If any entry error has been made, to correct such an error, draw a single straight line through the incorrect entry and enter the correct data above it. All such changes must be initialed and dated. DO NOT ERASE OR WHITE OUT ERRORS. For clarification of illegible or uncertain entries, print the clarification above the item, then initial and date it.

Access to study records will be limited to IRB-approved members of the study team. The investigator will permit study-related monitoring, audits, and inspections by the IRB/EC, the sponsor, government regulatory bodies, and University compliance and quality assurance groups of all study related documents (e.g., source documents, regulatory documents, data collection instruments, study data etc.). The investigator will ensure the capability for inspections of applicable study-related facilities (e.g., pharmacy, diagnostic laboratory, etc.).

Participation as an investigator in this study implies acceptance of potential inspection by government regulatory authorities and applicable University compliance and quality assurance offices.

An electronic database capture system will be created to record the data for this trial. Research coordinators will input clinical trial data into the database. This database is password protected and only the PI, assigned study team members, and CTO staff will have access to the database. DataCore, a core resource of the

Version: 1.23

May 2, 2022 Page 26

institution, will provide the primary data collection instrument for the study. All data requested in the system must be reported. All missing data must be explained. The quality assurance specialists will monitor this trial every 3 months for data entry accuracy.

REDCap (Research Electronic Data Capture) is a secure web application capture system that will be created to record the data for this study. This database is password protected; the PI and designated study team personnel will have access to the database. REDCap is the primary data collection instrument for this study. All data requested in the system must be reported. All missing data must be explained. The quality assurance specialists will monitor this trial every 3 months for data entry accuracy.

Source documentation refers to original records of observations, clinical findings, and evaluations that are subsequently recorded as data. Source documentation should be consistent with data entered into any electronic medical record or REDCap. Relevant source documentation to be reviewed by the DSMC throughout the study includes:

- 1. Baseline measures to assess pre-protocol status
- 2. Concurrent medications
- 3. Treatment records
- 4. Adverse events

Data Collection

Principal Investigator and IRB approved study personnel trained on this protocol will identify subjects. The following data elements will be captured from the subject's medical record and entered into the research database by the assigned data/research coordinator:

- age/ date of birth
- race
- MRN
- gender
- ethnicity
- participant enrollment location
- zip code

12 Quality Assurance and Quality Control

QC procedures will be implemented beginning with the data entry system and data QC checks that will be run on the database will be generated. Any missing data or data anomalies will be communicated to the site(s) for clarification/resolution.

Following written SOPs, the monitors will verify that the clinical trial is conducted, and data are generated, documented (recorded), and reported in compliance with the protocol, GCP, and the applicable regulatory requirements (e.g., Good Laboratory Practices (GLP), Good Manufacturing Practices (GMP)).

The investigational site will provide direct access to all trial related sites, source data/documents, and reports for the purpose of monitoring and auditing by the sponsor, and inspection by local and regulatory authorities.

This study will be monitored according to the monitoring plan detailed below. The Investigator will also ensure that the monitor or other compliance or quality assurance reviewer is given access to all the above noted study-related documents and study related facilities (e.g., pharmacy, diagnostic laboratory, etc.), and has adequate space to conduct the monitoring visit. A risk-based, data-driven monitoring approach will be used to verify data for this trial which will also include a centralized review of data for quality, trends, consistency, and general safety review. A quality assurance specialist will make regularly scheduled trips to the investigational site to review the progress of the trial, study data and site processes. At each visit, the monitor will review various aspects of the trial including, but not limited to: screening and enrollment logs; compliance with the protocol and study manual and with the principles of Good Clinical Practice;

May 2, 2022 Version: 1.23

Page 27

completion of case report forms; source data verification; study drug accountability and storage; facilities and staff.

During scheduled monitoring visits, the investigator and the investigational site staff must be available to meet with the quality assurance specialist in order to discuss the progress of the trial, make necessary corrections to case report form entries, respond to data clarification requests and respond to any other trialrelated inquiries of the monitor. In addition to on-site monitoring visits, the Sponsor and/or representatives will also be routinely reviewing data. Any queries identified through this review will be managed within the systems established for query resolution and tracking. Inquiries related to study conduct, which require further information or action will be discussed within the study team for appropriate and documented escalation plans. It is expected that response to data clarification requests and other trial-related inquiries will occur throughout the course of the study through regular communication with the site monitor, the Sponsor or representatives, and review/entry of data into the electronic study database.

At any time during the course of the study, representatives of regulatory agencies may review the conduct or results of the study at the investigational site. The investigator must promptly inform the IRB of any audit requests by health authorities and will provide sponsor with the results of any such audits and with copies of any regulatory documents related to such audits.

In accordance with HIPAA and associated privacy regulations, a patient's authorization to use personal identifiable health information may be required from each patient before commencement of research activities. This authorization document must clearly specify what parties will have access to a patient's personal health information, for what purpose and for what duration.

13 Ethics/Protection of Human Subjects

